## 3 Study Design

### **3.1 General Design**

This is a single-institution cohort study with two tiers. Tier 1 is an education study where participants can complete electronic surveys on their pre and post intervention confidence, perform two simulated patient encounters and have their documentation of electronic template monitored longitudinally over 12 months. Participants are free to opt out of any activity related to education assessment or system-based interventions to promote the use of learned skills (e.g. priming or profile feedback). Signed informed consent will Not be required for this tier.

Tier 2 is a behavioral study where participants, in addition to all of Tier 1 activities, also complete psychological inventories at three time points to measure emotion regulation and burnout, and participate in a semi-structured interview. We will require signed informed consent to participate in Tier 2.

**Figure 1** Study Design

Participant duration – each participant will be followed for 12 months beginning with their first communication training

### 3.2 Primary Study Endpoints

Resident, Fellow and Faculty template use at 12 months.

### 3.3 Secondary Study Endpoints

Resident, Fellow and Faculty post-intervention self-rated confidence and performance in simulated patient encounters.

## 4 Subject Selection and Withdrawal

### 4.1 Inclusion Criteria

All second-year internal medicine residents. All first-year hematology-oncology fellows.

### 4.2 Exclusion Criteria

Missed more than five days (out of 10 possible days) of the two week palliative care elective

### 4.3 Subject Recruitment and Screening

Designated study staff will make a brief presentation at a residency meeting (e.g. morning report) to advertise study, send emails and study members who do not have a role in evaluating residents or fellows will approach residents in person. Any resident who indicates they do not want to participate will not be approached again. Study staff who evaluate residents and fellows, specifically Drs. [name], [name] and [name], will not be involved in the recruitment or consenting process.

## **4.4 Early Withdrawal of Subjects**

### **4.4.1 When and How to Withdraw Subjects**

The scenarios we imagine when a study subject would withdraw is when he or she indicated to study staff that they no longer wanted to participate OR no longer. Verbal or electronic communication to the PI

### **4.4.2 Data Collection and Follow-up for Withdrawn Subjects**

We would continue to follow to participants' documentation over the 12 months from his or her initial training. If no longer working at study institution would follow documentation until last day of employment.

## **5 Study Procedures**

Please refer to Figure 1 – Study Design detailing study overview for the timing of interventions and assessments.

### **5.1 Before Communication Training Activities**

Tier 1 (education-only subjects): Three to four weeks prior to the subject's two-week palliative care elective they will be sent an email to complete an online confidence survey. They will receive email reminders to complete the survey until survey is completed.

Tier 2 (education + behavioral subjects): Subjects will have reviewed and signed consent documentation. In addition to the above online confidence survey, they will also receive email to complete electronic ERSQ and MBI.

### **5.2 Two week palliative care elective**

Tier 1 – Integrated into the two-week elective with the palliative care department, subjects undergo a 1) four-hour training focused on the SICG©; 2) two simulated patient encounters with trained actors and feedback provided after training, 3) participant sent electronic notification to take post intervention survey of confidence

Tier 2 – In addition to above, these subjects will also complete a Priming intervention. They will receive a list of patients whom 1) the study subjected documented at least one note on in the past and 2) have a high likelihood of serious illness as determined by a chart review process. This list will be shared securely through Dartmouth secure file electronically, and participants will be asked three questions for each patient: 1) "Does this patient have serious illness?"; 2) "Would you be surprised if this patient died in the next 12 months?"; 3) Would this patient benefit from a serious illness guide conversation?; 4) If you saw this patient again, would you use the serious illness conversation guide with him/ her? Subjects will be asked to review no more than 30 patients. Subjects will be asked to return the completed email via Dartmouth secure file share.

### **5.3 Electronic communication every two months following completion of elective**

Tier 1 – Every two months after completing the training, participants will receive email compare his or her own documentation of the taught template to top and average performers (comparison results given are anonymous). Non-top and top performers will receive different messages, customized through pre-testing with non-study residents and fellows. For example: "Talking to patients about their values is important but can take some pre-visit planning. Choose a patient you will see in the next two weeks to use the SICG" (non top-performers) or "Good job! Talking to

patients about their values is important. The way we continue to improve is by having more conversations. Choose a patient you will see in the next two weeks to use the SICG.” (top-performers). At four months, subjects will be asked electronically to complete their final confidence survey.

Tier 2 – For this part of the study, identical to Tier 1

#### **5.4 Semi-structured interviews**

Tier 2 only – Planned to occur about three months following training. Subjects are asked a series of questions designed to assess subject perception of serious illness communication, obstacles to implementing the training in practice, barriers to documentation and coaching sessions in real patient encounters with trained faculty. Interviews will be recorded, and expected duration is 20-40 minutes.

#### **5.5 Simulated Patient encounter at six months**

Tier 1 – Subject is contacted to arrange one-hour for simulated patient encounter, about 20-30 minutes for skill practice and the remainder for debrief. Subject has permission from program to have this hour to be away from their clinical duties.

Tier 2 – identical to Tier 1.

#### **5.6 Six and 12 month ERSQ and MBI assessment**

Tier 2 only – emails will be sent to participant to take ERSQ and MBI at month six and 12 following training

### **6 Statistical Plan**

#### **6.1 Sample Size Justification**

Primary Hypothesis: Template use for both trainee subgroups will increase from zero after training for  $\geq 50\%$  of trainee (Ha1a)

Let null hypothesis Hnull1a be  $p < 50\%$  and alternative hypothesis be Ha1a be  $p = p_1 \geq 50\%$ , where p is proportion of trainees who have any documented template use. Sample size of 42 (12 fellows and 30 eligible residents who have completed the education intervention by the end of the grant award period [June 2020]) enables us to have Minimum Detectable Difference (MDD) 19.05%, i.e., the least p1 is 69.05%, with 80% of power and 2.5% significance level using one-side proportion test with exact test.

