**Skills acquisition checklist** - used by independent observer during simulated patient encounters to evaluate trainees. One point is assigned for each item used by the trainee. The checklist contains three scores: conversation guide specific items (16 points), global communication skills (9 points), and a combined score (25 points). This checklist was developed internally and based on the experience training residents in the Serious Illness Conversation Guide (SICG).

**Template Use** –The analytics team at our institution is able to link the smartform to the physician who made alterations, the content of those alterations, patient and date of change.

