### **1.4 Prior Work**

Starting in 2017, we designed and implemented annual communication skills training. We trained 16 internal medicine residents (hereafter referred to as residents), 6 hematology-oncology fellows (hereafter referred to as fellows), and used a train-the-trainer model to train faculty attendings to serve as trainers in the clinical setting with trainees: 5 hospitalists, 4 primary care and 4 oncologists. We designed and embedded a template into the electronic medical record to standardize the documentation of the SICG. We developed a structured chart review protocol to identify outpatients with a high-likelihood of serious illness and evaluate trainee documentation habits

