## 2 Study Objectives

### **Aim 1. Evaluate the efficacy of our multimodal communication skills training on trainee documentation, confidence and observed communication skills over 12 months.**

Hypotheses: Template use for both trainee subgroups will increase from zero after training for ≥50% of trainees (Ha1a). Trainee and faculty confidence will increase after training for ≥50% of participants (Ha1b). Observed communication skills scores at the second and third simulated patient encounter will improve over the first encounter. (Ha1c).

Rationale: Augmenting standard training with priming, structured documentation templates, documentation audit and feedback, and embedded faculty coaches, we hope to increase the effect of communication skills training on clinical behavior change.

Outcomes: Participant template use at 12 months (Primary). Trainee, post-intervention self-rated confidence and performance in simulated patient encounters (Secondary).

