#### **6.2 Analysis Plan**

Primary Hypothesis: Ha1a

We will calculate the proportion of trainees with template use and provide 95% confidence intervals with exact method, then we will test the hypothesis using a proportion test.

Secondary Hypotheses

Ha1b: Trainee and faculty confidence will increase after training for  $\geq 50\%$  of participants.

We define increased confidence as trainee and faculty post-intervention confidence scores of 4 or 5 on a 5-point Likert scale. We will calculate proportion of subjects who have increased confidence and show 95% confidence intervals as well, then we will use a proportion test for the hypothesis.

**Ha1c: Observed communication skills scores at the second and third simulated patient encounter will improve over the first encounter.**

The observed communication skills scores have three different scores (two sub-scores and one combined/total score). We will apply a linear mixed model with random subject effect to test whether each of three scores are different from encounter 1 to 2 and 3 separately. P-values will be adjusted for multiple tests by the Dunnett method.

**Ha2a: Trainees in the top half of template users will have higher total emotion-regulation competences (TOTAL) than trainees in the bottom.**

The ERSQ yields 10 different scales of emotion regulation: 9 specific competences and 1 TOTAL competency which is the average of the nine scales. We will provide summary statistics (mean and standard deviation) of TOTAL competency and use a two-sample t-test to test differences between the top half and low half groups of patients. P-value will be presented.

**Ha2b: Trainees in the top half of template users will have lower Emotional Exhaustion (EE) scores than trainees in the bottom half.**

We will provide summary statistics (mean and standard deviation) of EE scores and use a two-sample t-test to test differences between the top half and low half groups of patients. P-value will be presented

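### The primary hypothesis is a rise in template use from zero, but the written plan does not check that use was zero before training, so a trainee who used it before and again afterwards would count as a rise from zero

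*Combined protocol and SAP*

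**What the plan says.** Section 2 (Aim 1) gives the primary hypothesis: "Template use for both trainee subgroups will increase from zero after training for ≥50% of trainees". Section 6.1 repeats it ("Template use for both trainee subgroups will increase from zero after training") and defines the tested quantity: "where p is proportion of trainees who have any documented template use". That definition contains no baseline value and no time window. Section 6.2 begins "We will calculate the proportion of trainees with template use", adds an exact 95% confidence interval and then applies a proportion test. Section 6.3 takes all trained residents and fellows as the population for the primary outcome.

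On whether zero can be assumed, section 1.4 reports annual training from 2017, with 16 residents, 6 fellows and 13 faculty (5 + 4 + 4) trained, and says "We designed and embedded a template into the electronic medical record to standardize the documentation of the SICG". The faculty were to act as trainers of trainees in clinical settings. Sections 4.1 and 4.2 do not exclude earlier users of the template. Section 3.1 follows each participant for 12 months from first training. Section 5.1 lists a confidence survey before training, plus the ERSQ and MBI in Tier 2, and no count of template use.

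On data, section 1.2 says the analytics team can link the smartform to the physician, the content of the change, and the "patient and date of change". Section 1.3 says the template also exists as a dotphrase.

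**The concern.** The hypothesis is about change and the test is about level. The two agree only if every trainee's use before training was zero. The study has one arm and no concurrent comparison, so the assumed zero is what lets a report of template use be read as a change in behaviour after training.

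Trainees could have met the template early, since it was in the record and both colleagues and supervising faculty had been trained. Anyone who used it then and kept using it would add to the numerator without any rise from zero. Enough such trainees could carry the observed proportion over the threshold when uptake among new users is only 50%, the boundary of the null hypothesis. Confidence is measured before training, but on the visible text the primary outcome is not.

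**Working it through.** **Inputs.** From section 6.1: "Sample size of 42 (12 fellows and 30 eligible residents who have completed the education intervention", so n = 42; null proportion 50%; one-sided exact test at 2.5%; 80% power; "Minimum Detectable Difference (MDD) 19.05" points, that is p1 = 69.05%. The documents give neither the share b of trainees with prior use nor the share c of those who continue after training. Both are assumed over a range.

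**The plan's own figure.** With X ~ Binomial(42, p):
- Threshold 28/42: P(X ≥ 28 | p = 0.50) = 0.0218, which meets 2.5%. Power at 69.05% is 69.7%, and 80% power needs p1 = 71.3%.
- Threshold 27/42: P(X ≥ 27 | p = 0.50) = 0.0442, which exceeds 2.5%. Power at 69.05% is 79.99%.

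The stated 69.05% therefore matches a one-sided 5% test, not the stated 2.5%. That is a separate matter. The rest of this check uses the stated 2.5% level and the threshold of 28.

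**Effect of continuing prior users.** Count only use after training, and let 50% of trainees with no prior use take up the template. The expected proportion is

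p = b·c + (1 − b)·0.5

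and the chance of declaring success is P(X ≥ 28 | 42, p).

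| Prior users b | Continue c | p | Chance of ≥ 28/42 |
|---|---|---|---|
| 0% | – | 0.500 | 2.2% |
| 10% | 50% | 0.10×0.50 + 0.90×0.5 = 0.500 | 2.2% |
| 10% | 75% | 0.10×0.75 + 0.90×0.5 = 0.525 | 4.5% |
| 10% | 100% | 0.10×1.00 + 0.90×0.5 = 0.550 | 8.5% |
| 20% | 50% | 0.20×0.50 + 0.80×0.5 = 0.500 | 2.2% |
| 20% | 75% | 0.20×0.75 + 0.80×0.5 = 0.550 | 8.5% |
| 20% | 100% | 0.20×1.00 + 0.80×0.5 = 0.600 | 23.6% |

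The error rate rises only when prior users continue more often than others start. The continuation rate matters as much as the prior-use rate.

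**What two possible remedies do to power.** Take k prior users, and uptake of 69.05% among the others.

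| k | Removed: n, threshold | Power if removed | Power if kept as failures, P(Bin(42 − k, 0.6905) ≥ 28) |
|---|---|---|---|
| 0 | 42, 28 | 69.7% | 69.7% |
| 2 | 40, 27 | 65.6% | 52.5% |
| 4 | 38, 26 | 61.0% | 33.6% |

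The removal columns use the exact one-sided 2.5% threshold for the reduced n.

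**The case against.** The strongest reply is that the plan means use after training. The hypothesis says so, and follow-up starts at first training. A reader might infer that anyone who had ever used the template counts as a success. On that reading of the plan this is wrong, because a trainee whose only use came before training is not counted. The problem is confined to trainees who used it before and again afterwards.

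A reader might also take 8.5% or 23.6% as the plan's real error rate. The documents do not support that. Those figures need 10% or 20% prior use and continuation by every prior user; at 50% continuation there is no inflation. Section 1.4 makes prior use possible but does not show it. The template records a specific guide that is taught in this training, and the earlier chart review of trainee documentation may be where the stated zero comes from. The documents do not settle this.

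Nor can one say that a baseline is certainly absent. Figure 1, to which section 5 refers for the timing of assessments, is not visible, and a record extract need not appear among participant procedures. Even so, section 6.2 uses no baseline.

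Two further limits stand. Section 1.2 describes linkage for the smartform only, so a zero from that source would not rule out earlier dotphrase use. And a confirmed zero would not by itself establish that training caused later use, since a single-arm cohort remains open to peer influence or a general change in practice.

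**Conclusion.** The point holds in limited form. The stated hypothesis needs a zero baseline, the analysis does not use or check one, and the visible text plans no check, although dated, physician-linked smartform data exist. A trainee with use both before and after training would be misclassified as a rise from zero.

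The size cannot be fixed from the documents. Over the assumed range of 10% to 20% prior use and 50% to 100% continuation, with 50% uptake among the others, the chance of declaring success runs from 2.2% (no inflation) to 23.6%. If nobody used the template beforehand, the primary result does not change. This does not show that the zero is false or that the trial's result would be wrong. The check is cheap and bears directly on the primary claim, so it should be made.

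**What to change.** In section 6.2:

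1. From the same smartform extract, obtain each trainee's template use from the date the template went live to the day before first training. Report the proportion with any use and its exact 95% CI.
2. State that use through the dotphrase alone may not be captured.
3. Define the primary endpoint as use on or after the date of first training.
4. Repeat the exact test among trainees with no pre-training use, the group in which use can rise from zero.
5. Do not keep prior users in the denominator as failures. That changes what is being estimated and, as shown above, costs far more power than removing them.

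The cost is an earlier start date on an existing data pull and a few sentences in 6.2, with no burden on participants. If prior users are found, the repeated analysis is smaller: power at 69.05% falls from 69.7% to 65.6% with two removed and 61.0% with four. If none are found, the result is unchanged and the stated zero is supported for smartform use.

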## Study Summary

Title	An Education and behavioral, single-center, Observational Cohort study evaluating the effect of emotion regulation and burnout on medical trainees' Learning and Documentation of serious illness communication
Short Title	Emotion Regulation and Burnout Impact on Communication Documentation
Protocol Number	The standard protocol number used to identify this study.
Phase	n/a
Methodology	Observation cohort Study
Study Duration	Two Years
Study Center(s)	Single-center: Dartmouth-Hitchcock Medical Center
Objectives	Aim 1. Evaluate the efficacy of our multimodal communication skills training on trainee documentation, confidence and observed communication skills over 12 months. Aim 2. Test the relationship between emotion regulation, and burnout on trainee skill enactment over 12 months.
Number of Subjects	42
Diagnosis and Main Inclusion Criteria	Internal Medicine Residents and Hematology-Oncology who undergo palliative care elective AND Serious Illness Communication training
Study Product, Dose, Route, Regimen	n/a
Duration of administration	n/a
Reference therapy	No gold standard for communication skills training
Statistical Methodology	one-side proportion test with exact test for primary outcome. Secondary outcomes use different statistical tests: 1) a linear mixed model with random subject effect to test whether three different scores in simulated encounters are different; 2) summary statistics, 3) t-tests

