### **6.3 Subject Population(s) for Analysis**

*Primary outcome is all residents and fellows trained. Secondary outcomes evaluating emotion regulation skill and burnout are in all residents and fellows who consented to be part of Tier 2 – the behavioral study part.*

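### Section 6.1 overstates power: with 42 trainees and an exact one-sided 2.5% test, power at 69.05% is 69.7%, not 80%, and the detectable difference at 80% power is 21.3 points, not 19.05

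*Combined protocol and SAP*

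**What the plan says.** Section 6.1 (Sample Size Justification) defines p as the proportion of trainees with any documented template use and sets the null boundary at 50%. It takes a "Sample size of 42 (12 fellows and 30 eligible residents who have completed the education intervention" by June 2020, and says that this number "enables us to have Minimum Detectable Difference (MDD) 19.05" percent, so that the smallest detectable rate is 69.05%, "with 80% of power and 2.5% significance level using one-side proportion test with exact test".

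The Study Summary names the same test: "one-side proportion test with exact test for primary outcome". For the same hypothesis, section 6.2 (Analysis Plan) will "provide 95% confidence intervals with exact method" and apply a proportion test, without giving a significance level. Section 6.3 defines the analysis set: "Primary outcome is all residents and fellows trained". No other section gives a power figure or qualifies this one.

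**The concern.** Section 6.1 gives every input to the calculation, so it can be checked without outside assumptions. The sample size, null value, test, level, alternative and power cannot all hold together.

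This is the plan's only power statement, and it concerns the primary hypothesis. The sample size is set by how many trainees are available, so the detectable difference is the main thing section 6.1 tells a reader. As printed, it implies a 20% chance of missing a true rate of 69.05%; at the stated level that chance is 30.3%.

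The mismatch also casts some doubt on which level was meant. Section 6.1 is the only place that gives a level for the primary test, and one possible result (27 of 42) passes at 5% and fails at 2.5%.

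**Working it through.** **Inputs, all from section 6.1.** n = 42 (12 + 30); null boundary p0 = 0.50; exact one-sided binomial test; level 0.025; p1 = 0.6905 (difference 0.1905); power 0.80.

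**Formulas.** The cut-off r is the smallest integer with P(X ≥ r | n, p0) ≤ level, where X is binomial. Power is P(X ≥ r | n, p1). The detectable rate is the p that solves P(X ≥ r | n, p) = 0.80.

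**Attempt to reproduce the plan's figure at the stated level.**

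| Cut-off r (of 42) | Size at p = 0.50 | Power at p = 0.6905 | Rate giving 80% power |
|---|---|---|---|
| 27 | 0.0442 | 0.7999 | 0.6905 |
| 28 | 0.0218 | 0.6972 | 0.7130 |

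A cut-off of 27 has size 4.42%, which exceeds 2.5%, so the 2.5% test must use 28. Then:

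- power at 69.05% = 69.7%, so type II error = 100 − 69.7 = 30.3%;
- the rate giving 80% power = 71.3%, so the detectable difference = 71.3 − 50 = 21.3 points.

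The plan's figure is not reproduced at 2.5%. It is reproduced in the first row, which is the exact test at one-sided 5%.

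**Could a different method at 2.5% explain it?** Power at 69.05% with n = 42, one-sided 2.5%:

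| Method | Power |
|---|---|
| Score test | 70.9% |
| Score test, continuity-corrected | 65.0% |
| Variance under the alternative | 76.1% |
| Variance under the alternative, continuity-corrected | 70.7% |
| Arcsine | 71.7% |

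None reaches 80%. The closest, using the variance under the alternative, reaches 80% only at a rate of 69.84%. A mid-p version of the exact test leaves the cut-off at 28, because the mid-p value at 27 is 0.033.

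**Could the figure be a count?** 29/42 = 69.05% and 8/42 = 19.05%, so the printed values also coincide with whole counts out of 42. This does not restore the power: at exactly 29/42 it is still 69.7%.

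**Link to the planned interval.** At 27/42 the exact one-sided p-value is 0.044 and the exact 95% lower limit is 48.0%, so 50% is not excluded. At 28/42 the lower limit is 50.5%. The 95% interval in section 6.2 therefore agrees with a one-sided 2.5% test and a cut-off of 28.

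**Other sample sizes, at one-sided 2.5% and 69.05%.** The 42 is a projection and everyone trained is analysed, so the achieved number may differ:

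| n | Cut-off | Power |
|---|---|---|
| 40 | 27 | 65.6% |
| 41 | 28 | 61.5% |
| 42 | 28 | 69.7% |
| 43 | 29 | 65.9% |
| 44 | 29 | 73.4% |

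Exact power first reaches 80% at n = 56 (cut-off 36, 82.1%). It dips just below again at 57 and 60 (79.5% each), and stays above 80% from 61 to 69, the largest size checked.

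**The case against.** The best defence is that little depends on the number. The sample size comes from trainee availability, not from a power target. The plan does not name 69.05% as an expected or important rate, and the hypothesis itself is about 50%. This is an uncontrolled single-centre cohort. Correcting the detectable difference moves it by 21.3 − 19.05 = 2.25 points, and the test, interval and type I error stay as they are. All of that is true. It limits the consequence, but it does not make the stated power correct.

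A second objection is that the documents do not show which figure is wrong. The 2.5% level appears once, and a 95% interval is a common reporting default, so it is only modest evidence for 2.5%. If 5% was intended, the 80% and the 19.05 points both stand and the level is the error. This is fair: the 5% origin is an inference, the match to 29/42 is another possible origin, and the authors must say which they meant. Either way, section 6.1 needs correcting.

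It would also go too far to say that the error changes a decision. At the stated 2.5%, 27/42 fails whatever section 6.1 says about power. The result would differ only if the test were run at 5%.

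**Conclusion.** The concern holds. At the stated exact one-sided 2.5% level with 42 trainees, power at 69.05% is 69.7%, about 10 points below the claim, and 80% power requires a true rate of 71.3% (difference 21.3 points). The result rests only on the inputs printed in section 6.1, with the test calibrated at the 50% boundary and all 42 trainees analysed. It does not depend on how the printed figure arose. The statement must be corrected because it is the only power claim and it covers the primary hypothesis. The error does not affect enrolment, the stated level, the exact 95% interval or type I error.

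**What to change.** The simpler course is to keep one-sided 2.5%, which agrees with the 95% exact interval in section 6.2, and to replace the power sentence in section 6.1 with wording such as:

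> With 42 trainees, an exact one-sided 2.5% test against 50% has 80% power if the true proportion is 71.3% (a difference of 21.3 percentage points); power at 69.05% is 69.7%. If 42 trainees are analysed, success requires at least 28 with template use. The cut-off will be recomputed for the number actually analysed.

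The last sentence is useful because 42 is a projection and section 6.3 analyses everyone trained.

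If one-sided 5% was intended, state that level in section 6.1, keep the 80% and 19.05 points (cut-off 27 of 42), and report a 90% exact interval in section 6.2 so that test and interval agree. The choice should be made and recorded before the primary data are examined.

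The first route costs one sentence, no extra participants, and a slightly less favourable stated detectable difference. The second also changes the interval in section 6.2.
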